11.6.1.2 Definition of serious adverse event

An SAE is any AE which:

- results in death
- is life-threatening (this refers to a reaction in which the patient was at risk of death at the time of the reaction; it does not refer to a reaction that hypothetically might had led to death if the reaction was more severe)
- requires in-patient hospitalisation or prolongation of existing hospitalisation
- results in persistent or significant disability/incapacity
- is a congenital anomaly/birth defect
- is an important medical event (IME) (this refers to a reaction that may not be immediately life-threatening or result in death or hospitalisation, but may jeopardise the patient or may require intervention to prevent any of the other outcomes defined above)

Examples of IMEs are intensive treatment in an emergency room for allergic bronchospasm or blood dyscrasias, convulsions that do not result in hospitalisation, development of drug dependency, and drug abuse.

Planned hospitalisations or surgical interventions for a condition that existed before the patient signed the ICF and that did not change in intensity are not SAEs.

If there is any doubt as to whether an AE meets the definition of an SAE, a conservative viewpoint must be taken, and the AE must be reported as an SAE.

11.6.1.3 Definition of adverse drug reaction

The term adverse drug reaction (ADR) is to be used whenever either the Investigator or Sponsor or designee assessed the AE as at least possibly related to the IMP.

11.6.1.4 Definition of serious adverse drug reaction

The term Serious Adverse Drug Reaction (SADR) is to be used whenever either the Investigator or Sponsor or designee assessed the SAE as at least possibly related to the IMP.

11.6.1.5 Definition of suspected unexpected serious adverse reaction

A SUSAR is any SADR whose nature or intensity is not consistent with the current Reference Safety Information (RSI) in the IB and therefore is assessed as unexpected.

11.6.1.6 Time period and frequency for collecting adverse events

All AEs (including SAEs) will be collected from the start of IMP administration (i.e. from the first placebo capsule given in association with breakfast to all patients at Visit 2) until the safety follow-up visit (Visit 6).

Any AE with start date of the day IMP administration must be recorded with start time.

At the safety follow-up visit (Visit 6), information on new AEs or SAEs, if any, and stop dates for ongoing events must be recorded as applicable.

CONFIDENTIAL 62 (92)

Clinical Study Protocol EP-002 Final version v3.0 12NOV2020

Investigators are not obligated to actively seek AEs or SAEs after conclusion of the study participation. However, if the Investigator learns of any SAE, including a death, at any time after a participant has been discharged from the study, and he/she considers the event to be reasonably related to the study intervention or study participation, the Investigator must promptly notify the Sponsor.

11.6.1.7 Assessment of intensity

The grading of the intensity of AEs will follow the common terminology criteria for adverse events (CTCAE) v5.0 [39]. Grade refers to the severity of the AE. The CTCAE displays Grades 1 through 5 with unique clinical descriptions of severity for each AE based on this general guideline.

The Investigator must assess the intensity of an AE using the following definitions, and record it on the AE Log in the eCRF:

- **Grade 1** Mild; asymptomatic or mild symptoms; clinical or diagnostic observations only; intervention not indicated.
- Grade 2 Moderate; minimal, local or non-invasive intervention indicated; limiting age-appropriate instrumental activities of daily living (ADL)*.
- Grade 3 Severe or medically significant but not immediately life-threatening; hospitalisation or prolongation of hospitalisation indicated; disabling; limiting self-care ADL**.
- **Grade 4** Life-threatening consequences; urgent intervention indicated.
- **Grade 5** Death related to AE.

11.6.1.8 Assessment of causal relationship

The Investigator must assess the causal relationship between an AE and the IMP using the definitions below and record it the AE Log of the eCRF:

- **Probable** The event has a strong temporal relationship to the IMP or recurs on rechallenge, and another aetiology is unlikely or significantly less likely.
- **Possible** The event has a suggestive temporal relationship to the IMP, and an alternative aetiology is equally or less likely.
- Unlikely The event has no temporal relationship to the IMP or is due to underlying/concurrent illness or effect of another drug (that is, there is no causal relationship between the IMP and the event).

An AE is considered causally related to the use of the IMP when the causality assessment is probable or possible.

CONFIDENTIAL 63 (92)

^{*}Instrumental ADL refer to preparing meals, shopping for groceries or clothes, using the telephone, managing money, etc.

^{**}Self-care ADL refer to bathing, dressing and undressing, feeding self, using the toilet, taking medications, and not bedridden.

Clinical Study Protocol EP-002 Final version v3.0 12NOV2020

11.6.1.9 Assessment of outcome

The Investigator must assess the outcome of an AE using the definitions below and record it on the AE Log of the eCRF:

Recovered/resolved The patient has recovered completely, and no symptoms remain.

Recovering/resolving The patient's condition is improving, but symptoms still remain.

Recovered/resolved with sequelae

The patient has recovered, but some symptoms remain (for example, the patient had a stroke and is functioning normally but

has some motor impairment).

Not recovered/not resolved

The patient's condition has not improved and the symptoms are unchanged (for example, an atrial fibrillation has become chronic).

Fatal

Unknown

11.6.1.10 Reporting of action taken with study treatment

The Investigator must report the action taken with study treatment using the definitions below and record it on the AE Log of the eCRF:

Dose increased

Dose not changed

Dose rate reduced

Dose reduced

Drug interrupted

Drug withdrawn

Not applicable

Unknown

11.6.1.11 Collecting adverse events

AEs identified using any of the following methods will be recorded:

- AEs spontaneously reported by the patient
- AEs observed by the Investigator or medical personnel
- AEs elicited based on non-leading questions from the Investigator or medical personnel

11.6.1.12 Recording adverse events

AEs must be recorded in the AE Log of the eCRF. The Investigator must provide information on the AE, preferably with a diagnosis or at least with signs and symptoms;

CONFIDENTIAL 64 (92)

Clinical Study Protocol EP-002 Final version v3.0 12NOV2020

start and stop dates, start and stop time; intensity; causal relationship to IMP; action taken, and outcome.

If the AE is serious, this must be indicated in the eCRF.

AEs, including out-of-range clinically significant clinical safety laboratory values, must be recorded individually, except when considered manifestations of the same medical condition or disease state; in such cases, they must be recorded under a single diagnosis.

11.6.1.13 Reporting of serious adverse events

SAE reporting should be performed by the Investigator within 24 hours of awareness via the eCRF. All available information regarding the SAE should be entered in the AE Log for the specific patient. By saving the event as "serious" in the eCRF and once the Investigator has signed-off of the event, an e-mail alert is automatically sent to predefined recipients to highlight that an SAE has been registered. The same information is automatically sent to [contact].

The SAE report is reviewed by a designated person at the CTC PV department to ensure that the report is valid and correct. For fatal or life-threatening SAEs where important or relevant information is missing, immediate follow-up is undertaken and queries to the site are raised. Investigators or other site personnel should inform CTC PV of any follow-up information on a previously reported SAE immediately but no later than within 24 hours of awareness.

If the SAE report in the eCRF is updated, a new e-mail alert will be sent.

If any additional documentation is required (e.g. autopsy report), CTC PV will request this information from the study site.

In case the eCRF cannot be accessed, the SAE should be reported by manual completion of the paper SAE Form, provided in the Investigator Site File (ISF). The completed, signed and dated paper SAE Form should, within 24 hours, be scanned and e-mailed to:

Medical Monitor: [name]

[contact]

E-mail: [contact]

Sponsor's medical representative: [name]

[contact]

E-mail: [contact]

A copy of the paper SAE form must also be e-mailed to CTC at: [contact], and to [contact].

The study site should notify the site Monitor via phone or e-mail about the submission of the SAE report. As soon as the site personnel have access to the eCRF, the SAE should be reported electronically as well.

The Sponsor or delegate will assume responsibility for reporting SAEs to the competent authority (CA) and independent ethics committee (IEC) in accordance with local regulations.

CONFIDENTIAL 65 (92)

11.6.1.14 Reporting of SUSARs to EudraVigilance, local CA and IEC

The term SADR is used whenever either the Investigator or Medical Monitor deems a blinded SAE as possibly or probably related to IMP. If an SADR is assessed as unexpected by the Medical Monitor, it is a potential SUSAR and under such circumstances an EudraVigilance reporter will be unblinded. In case the event is regarded as a SUSAR, the certified EudraVigilance reporter will report the SUSAR to the CA, via the EudraVigilance database, and to the IEC in accordance with local regulations and CTC SOPs within the following timelines:

- 7 calendar days if fatal or life-threatening (follow-up information within an additional 8 days)
- 15 calendar days if non-fatal and non-life-threatening (follow-up information as soon as possible)

The clock for expedited initial reporting (Day 0) starts as soon as the Sponsor becomes aware of an SAE. The date should be documented in an acknowledgement receipt.

The Medical Monitor is responsible for medical review of the SAE narrative in the Council for International Organisations of Medical Sciences (CIOMS) for (or equivalent) prior to expedited reporting.

The Sponsor or delegate is responsible for informing the Investigators concerned of relevant information about SUSARs that could adversely affect the safety of patients.

The Sponsor or delegate is responsible for once a year throughout the clinical study (or on request) submitting a safety report to the CA and the IEC taking into account all new available safety information received during the reporting period.

11.6.1.15 Treatment and follow-up of adverse events

Patients with AEs that occur during the study must be treated according to daily clinical practice at the discretion of the Investigator.

AEs must be followed up until resolution or to the safety follow-up visit (Visit 6), whichever comes first. At the safety follow-up visit, information on new AEs, if any, and stop dates for previously reported AEs must be recorded (if known). AEs assessed as stable by the Investigator at the safety follow-up visit will not have to be followed up until resolution.

It is the responsibility of the Investigator to follow up on all SAEs until the patient has recovered, stabilised, or recovered with sequelae, and to report to the Sponsor all relevant new information using the same procedures and timelines as those for the initial report. Relevant information includes discharge summaries, autopsy reports, and medical consultation.

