Each patient in the main part of the study will participate in the study for approximately 32 weeks including a screening period of up to 4 weeks, 26 weeks of treatment and a safety follow-up visit 2 weeks after the last treatment. Patients giving their consent to participate in a 6 month follow-up evaluation will participate in the study for 58 weeks including a screening period of up to 4 weeks, 26 weeks of treatment, a safety follow-up visit 2 weeks after the last treatment and a follow-up visit 26 weeks after the last treatment.

Efficacy assessments

Weight, other anthropometric measurements (BMI, waist circumference, sagittal diameter, bio-impedance), blood sampling for fasting lipid metabolism, glucose metabolism and inflammations markers, blood pressure, questionnaires (meal pattern, GSRS, satiety and craving, activity and sleep and health and quality of life [RAND-36]), drop-out rate (assessed both in terms of safety and efficacy).

Safety assessments

AE recording, vital signs (blood pressure assessed both in terms of safety and efficacy), ECG, fasting safety laboratory blood sampling, physical examination, GSRS (assessed both in terms of safety and efficacy).

Exploratory assessments

Fasting blood sampling for ApoA1 and ApoB, pre-dose blood sampling for orlistat and acarbose plasma concentrations at steady state. Weight, HbA1c and blood pressure 6 months after end of treatment.

Statistical methods

The primary endpoint, relative (%) change from baseline in body weight after 26 weeks of treatment with EMP16-02 (120 mg O/40 mg A) as compared to placebo, will be analysed using analysis of variance with treatment as independent variable.

The absolute change from baseline in body weight after 14 and 26 weeks of treatment with EMP16-02 (120 mg O/40 mg A) as compared to placebo will be analysed using analysis of covariance with treatment and body weight at baseline as covariates.

The relative (%) change from baseline in body weight after 14 and 26 weeks of treatment with EMP16-02 (150 mg O/50 mg A) as compared to placebo will be analysed using analysis of variance with treatment as independent variable. The relative and absolute change in body weight from baseline, and from end of treatment at 26 weeks, to 6 months after completion of the 26-week treatment period will be analysed by corresponding means.

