The side-effects experienced by both orlistat and acarbose are various gastrointestinal symptoms (such as flatulence, stomach rumblings, abdominal pain, increased defaecation, liquid and/or oily stools) as well as headache and nausea. Upper respiratory infections have also been reported to be more frequent with orlistat [15]. However, these side-effects are transient and will quickly resolve if patients stop taking the drugs. In rare cases, effects on the liver after taking acarbose have been reported [29]. For that reason, blood samples are taken at every visit to analyse liver function parameters.

Besides the risks related to the IMP as described above, there may also be risks related to the medical devices used in the study, for *e.g.*, venepuncture. However, these are devices that are

CONFIDENTIAL 25 (92)

Clinical Study Protocol EP-002 Final version v3.0 12NOV2020

used in routine medical care and the risk associated with their use is considered low and ethically justifiable. Study specific evaluations and sampling procedures, like blood pressure measurements using a blood pressure cuff and frequent blood sampling, may cause transient discomfort but the risk is deemed to be low and ethically justifiable.

Overall, the combined safety data from the previous phase IIa trial [28], and other pre-clinical and clinical studies, have not revealed any safety issues that would outweigh the expected benefits of the study. While keeping the above-mentioned risk factors at a minimum level in order to not expose the patients participating in the study for risks that would not be ethically justifiable, it is concluded that the planned study assessments are considered sufficient to meet the scientific and medical goals for the study. With regard to the substantial medical need for treatment of obesity, it is concluded that the potential benefits from the study will outweigh the potential risks for the treated patients.

More detailed information about the known and expected benefits and risks and reasonably expected adverse events (AEs) of EMP16-02 is found in current version of the IB.

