	Prior and concomitant med.	11.3.5				X			

CSP=Clinical study protocol, HIV=Human immunodeficiency virus.

- 1. For detailed schedule of events, see Table 8.1-4.
- 2. At Visit 6 or after early withdrawal.
- 3. Women of child-bearing potential (WOCBP) only, urine test.
- 4. Drug tests may also be performed at additional random occasions during the study.
- 5. Full safety laboratory profile: Clinical chemistry, haematology, coagulation, urinalysis (dip stick). Fasting is not required prior to Visit 1 and Visit 6.

6. Liver enzymes: ALT, AST, ALP, GGT.

CONFIDENTIAL 39 (92)

Clinical Study Protocol EP-002 Final version v3.0 12NOV2020

- 7. Visit 5: steady-state sample pre-dose.
- 8. To be filled in by the patient during, before or after the visits, and at the end of week 2, week 4, and week 8 to follow GI symptoms during the run-in phase.
- 9. To be filled in by the patient before breakfast (at the clinic), then once every hour until lunch (at home).
- 10. To be filled in by the patient at any hour on the day of Visit 2, and at Visit 5 at approximately the same hour (± 1h) as was done at Visit 2.
- 11. IMP administration at the clinic as follows:
 - Visit 2: Placebo capsule during breakfast at the clinic, first randomised IMP dose during lunch at home.
 - Visit 3 and Visit 4: IMP dose during breakfast at the clinic.
 - Visit 5: Last IMP dose during breakfast at the clinic.
- 12. Breakfast at the clinic after weight-related assessments and blood sampling. IMP taken during breakfast.
- 13. Visit 7 applicable for patients giving their separate consent to participate in the follow-up visit.
- 14. New Informed consent required before 6 months follow-up visit. Consent may be collected at any time point prior to any study assessments at Visit 7.
- 15. Visit 7: HbA1c only
- 16. Visit 7: blood pressure only

CONFIDENTIAL 40 (92)

Clinical Study Protocol EP-002 Final version v3.0 12NOV2020

Table 8.1-4 Detailed schedule of events for Visit 2 to 5

Category	Visit	Refer to									Visit 3	3 to 5			
		CSP Section	A	t the clini	ic		At home		At	At the clinic			At home		
	Assessment		Before breakfast	00:00	01.00	02:00	03:00	04:00	Before breakfast	00:00	01.00	02:00	03:00	04:00	
Screening and	Incl./excl. criteria	11.3.2	X												
demographics assessments	Brief physical examination	11.6.2.2	X						X						
	Alcohol breath test	11.3.7	X						X						
	Pregnancy test ¹	11.3.8	X						X						
Weight-related	Weight	11.4.1	X						X						

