9.8.3 Procedures for discontinuation of a patient from the study

A patient who prematurely discontinues participation in the study will always be asked about the reason(s) for discontinuation and the presence of any AEs. If a patient withdraws consent, the Investigator must ask the patient if he/she is willing, as soon as possible, to be assessed according to the procedures scheduled for the safety follow-up visit (Visit 6). Any ongoing AEs will be followed as described in Section 11.6.1.15.

The primary reason for discontinuation/early withdrawal must be specified in the eCRF and final drug accountability must be performed.

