10.3 Conditions for storage

Both EMP16-02 60/20 and EMP16-02 90/30 capsules should be stored in the fridge (2°C to 8°C) to prolong stability to up to 12 months. Single capsules can be stored at room temperature for a maximum of 12 h.

At temperatures above 40°C, the G3 fraction containing or listat can melt, which may affect the granulation of the fraction and as such the release of or listat and the efficacy of the IMP. This may result in gastrointestinal symptoms. No toxic degradation products have been observed in stability tests.

10.4 **Preparation and accountability**

Each site and the Investigator will maintain a Storage and Accountability Log as well as a Drug Dispensing Log detailing the dates and quantities of study medication received and used by each patient, and study medication destroyed at the safety follow-up visit (Visit 6). Any discrepancies between prepared and returned IMP must be explained and documented. Products deliberately and/or accidentally destroyed by the site or the patient must be accounted for.

CONFIDENTIAL 54 (92)

10.5 **Treatment administration**

The patients will be treated with IMP for a period of 26 weeks.

At the clinic, the IMP will be dispensed by site staff, *e.g.*, a study nurse, directly from the individually packed boxes. At home, the patients will self-administer the IMP. The IMP should be taken halfway into a meal, with approximately 100-200 mL water or other drink. The patient should be instructed to not take more than 200 mL water or other drink during the meal, as this can affect the efficacy of the IMP.

The IMP should preferably be taken halfway through each of the three main meals during the day, but can be taken up to 1 hour after the meal. If a dose of EMP16-02 is missed more than 1 hour from the start of the meal, the dose should not be taken. The IMP should not be taken on an empty stomach. If the patient is not eating three main meals on a day, the IMP can be taken with a lighter snack as well. The patients will be recommended to leave 3-4 h between each meal/IMP dose.

The first IMP dose will be taken at home in association with lunch (or other main meal following breakfast) on Day 1 (after Visit 2). One placebo capsule will be given to all patients in association with breakfast at the clinic on Day 1 (Visit 2).

The last dose will be taken at the clinic in association with breakfast on Day 179±3 days (Visit 5, week 26; in total one dose on Day 179).

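### Visit 6 closes adverse event collection and non-serious follow-up, but after early discontinuation it has no minimum time from the last dose, so early leavers can be observed for less time than completers

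*Protocol*

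**What the plan says.** **What Visit 6 closes.** Section 11.6.1.6 has AEs collected from the first capsule at Visit 2 "until the safety follow-up visit (Visit 6"). For follow-up, Section 11.6.1.15 says "AEs must be followed up until resolution or to the safety follow-up visit (Visit 6), whichever comes first". The same section then says that AEs the investigator judges stable at that visit need not be followed to resolution. Serious AEs are followed to recovery or stabilisation, whatever the date of Visit 6.

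**When Visit 6 falls for completers.** The Synopsis describes "26 weeks of treatment and a safety follow-up visit 2 weeks after the last treatment". Section 10.5 says "The last dose will be taken at the clinic in association with breakfast on Day 179±3 days", and Table 8.1-3 puts Visit 6 on Day 193, also with a window of 3 days either way.

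**When Visit 6 falls for early leavers.** Footnote 2 of Table 8.1-3, attached to the Visit 6 column, reads "At Visit 6 or after early withdrawal". Section 9.8.3 says that a patient who withdraws consent must be asked about willingness, "as soon as possible, to be assessed according to the procedures scheduled for the safety follow-up visit (Visit 6"). It sends any AE ongoing at discontinuation to Section 11.6.1.15. Section 9.8.1 lists significant AEs as a reason for discontinuation separate from withdrawal of consent.

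**Liver stops.** Section 9.8.2 schedules a visit corresponding to Visit 6 about four weeks after treatment stops. Its next paragraph describes the safety follow-up visit as two weeks after the end of treatment.

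**The concern.** A visit that closes safety observation should fall at a comparable time after the last dose for everyone whose data are compared. Here the closing rule is fixed to a visit, and that visit can move. Completers have it about two weeks after their last dose. Patients who stop early can have it at any time after withdrawal. Read as written, Sections 11.6.1.6 and 11.6.1.15 then let AE collection and non-serious follow-up stop on that day.

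Three things are at stake:

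- **Comparability between arms.** If drop-out differs by arm, so does the average length of post-dose AE observation. Drop-out, overall and GI-related, is itself a secondary endpoint, and its relation to tolerability is a secondary objective.
- **A claim that may go unchecked.** Section 6.3 states that "these side-effects are transient and will quickly resolve if patients stop taking the drugs". The patients who stopped because of side effects are those in whom this could best be seen, yet follow-up may end before resolution is recorded.
- **Few other records after stopping.** The GI symptom questionnaire is scheduled up to Visit 5 and not at Visit 6 (Tables 8.1-3 and 11.5-2). Under Section 11.6.1.1, listed GI symptoms become AEs only if severe, and the investigator confirms the intensity at the next scheduled visit. For an early leaver that may be the same visit that closes collection.

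**Working it through.** **Inputs.** Last dose on Day 179 ± 3 (Section 10.5); Visit 6 on Day 193 ± 3 (Table 8.1-3); 156 randomised, 52 per arm (Sections 9.3 and 9.9); drop-out 20% (Section 17.2).

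**Step 1: reproduce the plan's interval for completers.**

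- Nominal: 193 − 179 = 14 days, which agrees with the stated two weeks.
- Shortest, with both windows applied to the study-day calendar: (193 − 3) − (179 + 3) = 190 − 182 = 8 days.
- Longest: (193 + 3) − (179 − 3) = 196 − 176 = 20 days.

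**Step 2: the interval for early leavers.** The protocol gives none outside the liver criteria. Suppose the Visit 6 procedures take place *k* days after the last dose and close AE collection. The post-dose window is then *k* days, and the shortfall against a completer's nominal window is 14 − *k*. The values of *k* are assumptions that show the range.

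| *k* (days, assumed) | Post-dose window | Shortfall against 14 days |
|---|---|---|
| 0 | 0 | 14 |
| 1 | 1 | 13 |
| 3 | 3 | 11 |
| 7 | 7 | 7 |
| 14 | 14 | 0 |

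Nothing in footnote 2 or Section 9.8.3 rules out the top rows or requires the bottom one.

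**Step 3: the liver rule.** Four weeks is 28 days, or 28 − 14 = 14 days more than a completer has. The two-week wording in the same section gives 14 days, the same as a completer. The section does not say which applies.

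**Step 4: how many patients.** 0.20 × 156 = 31.2 in total; 0.20 × 52 = 10.4 per arm. This is drop-out for any reason, so it is an upper bound on those affected at the planned rate.

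**Step 5: the passages side by side.**

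| Type of early stop | Timing of Visit 6 | What ends AE observation |
|---|---|---|
| Withdrawal of consent | Promptly, if willing (9.8.3) | Visit 6 (11.6.1.6, 11.6.1.15) |
| Non-serious AE, investigator's decision | After withdrawal, no interval (footnote 2) | Visit 6 (same sections) |
| Serious AE | After withdrawal, no interval (footnote 2) | Recovery or stabilisation for that event (11.6.1.15) |
| Liver criteria | About 4 weeks and also 2 weeks (9.8.2) | Visit 6, then referral if enzymes have not returned to baseline |

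Within Section 11.6.1.15, ending follow-up at the earlier of resolution and Visit 6 sits beside a sentence releasing only stable AEs from follow-up to resolution. The second implies that AEs not yet stable are followed further; the first says they are not.

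**The case against.** The strongest reply is that the closing point may not move at all. The Synopsis and Section 8.1 define the safety follow-up visit as two weeks after the last dose. Section 9.8.3 asks only for the procedures of Visit 6 and does not say that AE collection then ends. On that reading the withdrawal visit is an extra safeguard. This is a fair reading, but footnote 2 assigns the Visit 6 column itself to the time after early withdrawal, which supports the other one. Sites could follow either.

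A reader might also infer that patients who leave because of an AE get the shortest observation of all, or that their follow-up stops a day after the last dose. The documents do not support this. The prompt visit is written for patients who withdraw consent, and seeing them while they are still willing is sensible. No interval, short or long, is set for AE discontinuations. Serious AEs are followed beyond Visit 6, related serious AEs learned of later must still be notified, and one sentence of Section 9.8.2 gives liver stops a longer interval than completers have. A window of zero or one day is what the wording permits, not a protocol figure.

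The consequences are also limited. The AE endpoint concerns the 26 weeks of treatment, the AE analysis in Section 17.7.1 is descriptive, and time to resolution is not an endpoint. That lowers the weight of the point. It does not remove the missing anchor or the conflicting passages.

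**Conclusion.** The point holds in a limited form. Visit 6 ends AE collection and non-serious follow-up. For completers it comes 14 days after the last dose (8 to 20 with windows); for early discontinuation outside the liver criteria it has no minimum distance from the last dose. Early leavers, including those stopped for a non-serious AE, can therefore be observed for less time than completers, and unequally between arms if drop-out differs.

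The size is at most about 31 of 156 patients, or about 10 per arm. This assumes the planned 20% drop-out, counts every reason for leaving, and leaves out any replacements under Section 9.8.4. Some of these patients would attend no visit. The share leaving for AEs is not given, so the number of AE leavers with a shortened window cannot be computed. The shortfall per patient can be anything from none to the full 14 days, depending on when the site holds the visit.

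Two contradictions stand regardless of these assumptions: the two timings for one visit in Section 9.8.2, and the two follow-up rules in Section 11.6.1.15.

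**What to change.** Reconcile Sections 9.8.2, 9.8.3, 11.6.1.6 and 11.6.1.15 with footnote 2 of Table 8.1-3:

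- For every type of early discontinuation, not only withdrawal of consent, tie the end of AE collection and of non-serious AE follow-up to the last dose, not to the date of the withdrawal visit. The basis should be consistent with that for completers and with the liver rule.
- Resolve the two timings of the safety follow-up visit in Section 9.8.2.
- State in Section 11.6.1.15 whether an AE that is not yet stable at Visit 6 is followed further.
- Keep the prompt withdrawal visit, and say explicitly whether it closes anything.
- Record patients who refuse further contact as such.

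The interval is for the sponsor to decide; none is proposed here. The cost is protocol wording plus at most one brief contact per early leaver, so about 31 contacts at the planned drop-out.
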